7.1.5.2 Treatment Period

The following assessments will be performed on day 1 of each cycle and must be performed no more than 24 hours prior to treatment unless otherwise specified. The only exception is for day 1 when the assessments will serve as baseline assessments and can be performed up to 3 weeks prior or as otherwise specified.

- 1. Adverse event review
- 3. Directed physical examination
- 4. Vital signs and weight
- 5. ECOG performance status
- 5. CBC
- 6. Comprehensive serum chemistry panel
- 6. Tumor Assessments of known sites of disease (every 9 weeks; 63 +/- 7 days)

7.1.5.3 Post-Treatment Visits

7.1.5.3.1 Safety Follow-Up Visit

The mandatory Safety Follow-Up Visit should be conducted approximately 30 days after the last dose of trial treatment or before the initiation of a new anti-cancer treatment, whichever comes first. All AEs that occur prior to the Safety Follow-Up Visit should be recorded.

7.1.5.4 Follow-up Visits

Subjects who discontinue trial treatment for a reason other than disease progression will move into the Follow-Up Phase and should be assessed every 8 weeks (56 ± 7 days) by radiologic imaging to monitor disease status. Every effort should be made to collect information regarding disease status until the start of new anti-neoplastic therapy, disease progression, death, end of the study or if the subject begins retreatment with MK-3475 as detailed in Section 7.1.5.2.1. Information regarding post-study anti-neoplastic treatment will be collected if new treatment is initiated.

Subjects who are eligible to receive retreatment with MK-3475 according to the criteria in Section 7.1.5.2.1 will move from the follow-up phase to the Second Course Phase when they experience disease progression. Details are provided in Section 6.2 - Trial Flow Chart for Retreatment.

7.1.5.4.1 Survival Follow-up

Once a subject experiences confirmed disease progression or starts a new anti-cancer therapy, the subject moves into the survival follow-up phase and should be contacted by telephone every 12 weeks to assess for survival status until death, withdrawal of consent, or the end of the study, whichever occurs first.

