After the end of treatment, each patient will be followed for a minimum of 30 days for adverse event monitoring (serious adverse events will be collected for up to 90 days after the end of treatment). Subjects will have post-treatment follow-up for disease status until death, withdrawing consent, or becoming lost to follow-up.

Participation in this trial will be dependent upon supplying tumor tissue from either a newly obtained formalin-fixed specimen, or an older formalin-fixed, paraffin-embedded specimen from locations not radiated prior to biopsy. Newly obtained formalin-fixed specimens are strongly encouraged unless clinically contraindicated as deemed by the treating physician. If new scientific data emerge that indicate that an existing biopsy or surgical specimen is suboptimal for identification of patients, only new biopsies will be acceptable for determination of PD-L1 status. The specimen will be evaluated at a central laboratory facility for expression status of PD-L1 in a prospective manner.

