4.2.3 Rationale for Endpoints

Both vorinostat and MK-3475 appear to be well tolerated as a single agents and have FDA approved doses and indications. These two drugs have non-overlapping mechanisms of action. There has been no reported clinical experience with the combination of vorinostat and MK-3475. Therefore a phase I/II design, wherein a limited phase I run in cohort is initially enrolled, was felt to be most appropriate to study this combination, with safety and tolerability as the primary endpoint of interest.

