Events of clinical interest of a potential immunologic etiology (irECIs) may be defined as an adverse event of unknown etiology, associated with drug exposure and is consistent with an immune phenomenon. irAEs may be predicted based on the nature of the MK-3475 compound, its mechanism of action, and reported experience with immunotherapies that have a similar mechanism of action. Special attention should be paid to AEs that may be suggestive of potential irAEs. An irAE can occur shortly after the first dose or several months after the last dose of treatment.

If an irAE is suspected, efforts should be made to rule out neoplastic, infectious, metabolic, toxin or other etiologic causes prior to labeling an adverse event as an irAE. Information on how to identify and evaluate irAEs has been developed and is included in the Pembrolizumab Event of Clinical Interest Guidance Document.Subjects who develop a Grade 2 or higher irAE should be discussed immediately with the Sponsor.

Recommendations to managing irAEs not detailed elsewhere in the protocol are detailed in Table 6.

irAE	Withhold/Discontinue MK- 3475?	Supportive Care
Grade 1	No action	Provide symptomatic treatment
Grade 2	May withhold MK-3475	Consider systemic corticosteroids in addition to appropriate symptomatic treatment
Grade 3 and Grade 4	Withhold MK-3475 Discontinue if unable to reduce corticosteroid dose to < 10 mg per day prednisone equivalent within 12 weeks of toxicity	Systemic corticosteroids are indicated in addition to appropriate symptomatic treatment. May utilize 1 to 2 mg/kg prednisone or equivalent per day. Steroid taper should be considered once symptoms improve to Grade 1 or less and tapered over at least 4 weeks.

Table 6 General Approach to Handling irAEs

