6.0 TRIAL FLOW CHART FIRST COURSE OF TREATMENT

Trial Period:			Treatr	nent C	ycles					End of Treatment		Post-Treatment	
	Screening	1			4	To b		ted bey cles	ond 8		Safety		Surviva
Treatment Cycle/Title:			2	3		5	6	7	8	Discon	Follow- up	Follow Up Visits	Follow- Up
Scheduling Window (Days):	-28 to 1		± 3	± 3	± 3	± 3	± 3	± 3	± 3	At time of Discon	30 days post discon	Every 8 weeks post discon	Every 12 weeks
Informed Consent	Х												
Inclusion/Exclusion Criteria	Х												
Demographics and Medical History	Х												
Trial Treatment Administration		Х	Х	Х	Х	Х	Х	Х	Х				
Survival Status													Х
Review Adverse Events		Х	Х	Х	Х	Х	Х	Х	Х	Х	Х		
Full Physical Examination	Х												
Directed Physical Examination		Х	Х	Х	Х	Х	Х	Х	Х	Х	Х		
Vital Signs and Weight	Х	Х	Х	Х	Х	Х	Х	Х	Х	Х			
ECOG Performance Status	Х	Х	Х	Х	Х	Х	Х	Х	Х	Х			
Pregnancy Test – Urine or Serum β -HCG	X ^a												
PT/INR and aPTT	Х												
CBC	Х	Х	Х	Х	Х	Х	Х	Х	Х	Х	Х		
Comprehensive Serum Chemistry Panel (see 7.1.3.1)	Х	Х	X	X	X	X	X	Х	X	Х	Х		
Urinalysis	Х												
T3, FT4 and TSH	Х												
Tumor Imaging (see section 7.1.2.6)	Х				Х		Х						
Archival or Newly Obtained Tissue Collection (see section 7.1.2.7)	Х				Х								

Trial Period:		Treatment Cycles						End of Treatment		Post-Treatment			
	Screening	1			4	To b	~	ted beyo cles	ond 8	Safety		5	
Treatment Cycle/Title:			2	3		5	6	7	8	Discon	Follow- up	Follow Up Visits	Follow- Up
Scheduling Window (Days):	-28 to 1		± 3	± 3	± 3	± 3	± 3	± 3	± 3	At time of Discon	30 days post discon	Every 8 weeks post discon	Every 12 weeks
Correlative Studies Blood Collection (see section 7.1.2.7)	Х				Х					Х			

Confidential 📀 Limited Access

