7.2 Assessing and Recording Adverse Events

An adverse event is defined as any untoward medical occurrence in a patient or clinical investigation subject administered a pharmaceutical product and which does not necessarily have to have a causal relationship with this treatment. An adverse event can therefore be any unfavorable and unintended sign (including an abnormal laboratory finding, for example), symptom, or disease temporally associated with the use of a medicinal product or protocol-specified procedure, whether or not considered related to the medicinal product or protocol-specified procedure. Any worsening (i.e., any clinically significant adverse change in frequency and/or intensity) of a preexisting condition that is temporally associated with the use of the Merck's product, is also an adverse event.

Changes resulting from normal growth and development that do not vary significantly in frequency or severity from expected levels are not to be considered adverse events. Examples of this may include, but are not limited to, teething, typical crying in infants and children and onset of menses or menopause occurring at a physiologically appropriate time.

Merck product includes any pharmaceutical product, biological product, device, diagnostic agent or protocol-specified procedure, whether investigational (including placebo or active comparator medication) or marketed, manufactured by, licensed by, provided by or distributed by Merck for human use.

Adverse events may occur during the course of the use of Merck product in clinical trials or within the follow-up period specified by the protocol, or prescribed in clinical practice, from overdose (whether accidental or intentional), from abuse and from withdrawal.

Adverse events will be recorded from the time the first dose of either vorinostat or MK-3475 is administered through 30 days following cessation of treatment and at each examination on the Adverse Event case report forms/worksheets. After 30 days, adverse events related to either MP-3475 or vorinostat will be followed until resolution or stabilization of the AE or until the beginning of a new anti-neoplastic therapy, whichever occurs first. The reporting timeframe for adverse events meeting any serious criteria is described in section 7.2.3.1.

Only adverse events that meet the following definition will be recorded.

- All grade 3 and higher adverse events

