7.2.3 Immediate Reporting of Adverse Events to the Sponsor and to Merck

7.2.3.1 Serious Adverse Events

A serious adverse event is any adverse event occurring at any dose or during any use of Merck's product that:

- Results in death;
- Is life threatening;
- Results in persistent or significant disability/incapacity;
- Results in or prolongs an existing inpatient hospitalization;
- Is a congenital anomaly/birth defect;
- Is a new cancer (that is not a condition of the study);
- Is associated with an overdose;
- Is another important medical event
- Overdose

Refer to Table 10 for additional details regarding each of the above criteria.

Progression of the cancer under study is not considered an adverse event unless it results in hospitalization or death.

Any serious adverse event, or follow up to a serious adverse event, including death due to any cause other than progression of the cancer under study that occurs to any subject from the time the consent is signed through 90 days following cessation of treatment, or the initiation of new anti-cancer therapy, whichever is earlier, whether or not related to Merck product, must be reported within 24 hours to the Sponsor and within 2 working days to Merck Global Safety.

Non-serious Events of Clinical Interest will be forwarded to Merck Global Safety and will be handled in the same manner as SAEs.

Additionally, any serious adverse event, considered by an investigator who is a qualified physician to be related to Merck product that is brought to the attention of the investigator at any time outside of the time period specified in the previous paragraph also must be reported immediately to the Sponsor and to Merck.

SAE reports and any other relevant safety information are to be forwarded to the Merck Global Safety [contact]

A copy of all 15 Day Reports and Annual Progress Reports is submitted as required by FDA, European Union (EU), Pharmaceutical and Medical Devices agency (PMDA) or other local regulators. Investigators will cross reference this submission according to local regulations to the Merck Investigational Compound Number (IND, CSA, etc.) at the time of submission.

Additionally investigators will submit a copy of these reports to Merck & Co., Inc. (Attn: Worldwide Product Safety; [contact]) at the time of submission to FDA.

All subjects with serious adverse events must be followed up for outcome.

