related event. Subjects who develop an ECI thought to be immune-related should have additional testing to rule out other etiologic causes. If lab results or symptoms indicate a possible immune-related ECI, then additional testing should be performed to rule out other etiologic causes. If no other cause is found, then it is assumed to be immune-related.

ECIs that occur in any subject from the date of first dose through 90 days following cessation of treatment, or the initiation of a new anticancer therapy, whichever is earlier, whether or not related to the Merck's product, must be reported within 24 hours to the Sponsor and to Merck Global Safety within 2 working days.

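### SAEs and ECIs are reportable to 90 days after treatment, but the last scheduled adverse event review is at about day 30, so late immune toxicity is likely to be under-counted

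*Combined protocol and SAP*

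**What the plan says.** **Status of safety.** Section 4.2.3 describes the design "with safety and tolerability as the primary endpoint of interest". Section 8.2 reports toxicity as numbers and percentages of patients.

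**Reporting windows.** Section 2.1.2 states that "serious adverse events will be collected for up to 90 days after the end of treatment". Section 7.2.3.1 requires SAE reports "from the time the consent is signed through 90 days following cessation of treatment, or the initiation of new anti-cancer therapy, whichever is earlier". Section 7.2.3.2 covers "ECIs that occur in any subject from the date of first dose through 90 days following cessation of treatment", with the same early close at new therapy. For adverse events in general, Section 7.2 records from the time the first dose "is administered through 30 days following cessation of treatment".

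**Scheduled contacts.** In flow charts 6.0 and 6.1 the row "Review Adverse Events" is marked at cycles 1 to 8, at discontinuation and at the 30-day safety visit, and nowhere later. Section 7.1.5.3.1 gives the same end point. Section 7.1.5.4 uses the 8-weekly visits (56 ± 7 days) for imaging and disease status. Under Section 7.1.5.4.1, patients with confirmed progression or new therapy "should be contacted by telephone every 12 weeks to assess for survival status until death, withdrawal of consent, or the end of the study".

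**Expected timing.** Section 5.6.1.1 says of immune-related events: "An irAE can occur shortly after the first dose or several months after the last dose of treatment".

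**The concern.** The plan sets a reporting duty to day 90 but schedules its last look for adverse events at about day 30. A site that follows the schedule exactly has no planned occasion on days 31 to 90 to ask a patient about a new event. The protocol itself expects some immune-related events to start in that period or later.

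Section 8.2 makes no adjustment for incomplete ascertainment, so each missed event lowers a reported frequency directly. Section 4.2.3 says there is no reported clinical experience with this combination, and Section 4.1.2 says the safety data will help decide whether to study it further. What is at stake is whether uncommon late events are seen at all.

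**Working it through.** **1. The plan's own precision figure.** Section 8.1 says 35 patients estimate a frequency to within 17% with 95% confidence. Half-width at p = 0.5: 1.96 × √(0.5 × 0.5 / 35) = 0.166, or 17 points when rounded. The figure reproduces. It describes sampling error only and makes no allowance for events that occurred but were not found.

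**2. Length of the gap.** Inputs are the 90-day window (7.2.3.1, 7.2.3.2) and the last review at about day 30 (7.1.5.3.1, flow charts).

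- No new therapy by day 90: 90 − 30 = 60 days; 60/90 = 67%.
- New therapy on day T, between day 30 and day 90: the gap is T − 30 days. For example, T = 60 leaves 30 of 60 days (50%).
- New therapy by day 30: Sections 7.1.1.5.3 and 7.1.5.3.1 put the safety visit before it, so there is no gap.

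The 67% is therefore a maximum.

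**3. What falls inside the gap.**

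| Contact | Timing | Stated content |
|---|---|---|
| 8-weekly visit (no progression) | day 49 to 63 after discontinuation, then about day 112 | imaging, disease status |
| 12-weekly call (progression or new therapy) | anchor not stated | survival status |
| ECI assessment (7.2.3.2) | before each dose | ends with dosing |
| Chemistry panel (flow charts) | last at the 30-day visit | laboratory safety |

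If the call is counted from the last dose it falls on day 12 × 7 = 84, six days before the window closes. If it is counted from the 30-day visit it falls on day 30 + 84 = 114, after the window. Either way its stated purpose is survival status.

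The blank flow-chart cells are weak evidence alone, because imaging is not marked in the follow-up column either although Section 7.1.5.4 requires it. Sections 7.1.5.3.1 to 7.1.5.4.1 show the same gap in prose.

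One ECI in Section 7.2.3.2 is defined by liver tests. With no chemistry panel scheduled after day 30, a case without symptoms in that period could not be volunteered by the patient.

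**4. Possible size, by assumption.** The documents give neither a late-event rate nor a rate of passive detection. Let p be the share of patients with a reportable event on days 31 to 90, and s the share of those events that passive capture finds. The expected number found in n patients is n × p × s. The chance of finding at least one is 1 − (1 − p × s)^n. All values of p and s below are assumed.

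| p | Expected events in 70 patients, s = 100 / 75 / 50 / 25% | Chance of at least one in a cohort of 35, same s |
|---|---|---|
| 2% | 1.4 / 1.05 / 0.70 / 0.35 | 51 / 41 / 30 / 16% |
| 5% | 3.5 / 2.6 / 1.75 / 0.88 | 83 / 74 / 59 / 36% |
| 10% | 7.0 / 5.25 / 3.5 / 1.75 | 97 / 93 / 83 / 59% |

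At p = 5% and s = 50%, a frequency shifts by 5 − 2.5 = 2.5 points, well below the 17-point sampling margin. The chance of seeing any such event in a cohort falls from 83% to 59%. The loss falls mainly on detecting rare late events rather than on estimating common toxicities.

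**The case against.** The strongest reply is that the plan does not abandon these events. SAE and ECI reporting is mandatory to day 90. Section 7.1.2.1 has adverse events recorded during follow-up and assessed more often when clinically indicated. Section 7.2 records at each examination and follows related events past day 30 until they resolve or stabilize. An imaging visit or a telephone call may bring an event to light. Detailed ECI guidance sits in a separate document (Appendix 12.8) that is not available here.

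Part of this stands. Capture after day 30 is passive rather than absent, and the missing guidance might help. But Section 7.1.2.1 ties routine assessment to the flow chart, and following a known event to resolution does not find a new one. None of these provisions schedules a contact.

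A reader might also infer four stronger points that the documents do not support:

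- **A 67% gap for every patient.** Patients who stop for progression may start new therapy, which closes their window. For the same reason it cannot be shown that the under-count is worst in them, although the others at least attend an imaging visit inside the window.
- **A first survival call on day 84.** That rests on an anchor the plan does not give.
- **A direct contradiction that leaves a non-serious ECI on day 60 unrecordable.** Section 7.2 lists ECIs among the events to record, Section 7.2.3.1 handles non-serious ECIs in the same way as SAEs, and Section 7.2.3.2 requires them on the adverse event forms. Read together, such an event is recorded; Section 7.2 only needs to say so.
- **Harm to the run-in decision.** The dose-limiting toxicity rule uses cycle 1 alone.

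**Conclusion.** The point holds. The reporting duty runs up to 60 days beyond the last scheduled adverse event review, and no stated contact in that interval is used to look for new events. The direction of the error is clear: missed events can only lower the toxicity frequencies. The under-count is likely rather than certain, and its size cannot be derived from the documents. The figures in the table illustrate assumed rates and are not estimates for this trial.

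The conclusion rests on reading the stated purpose of the later contacts as their full content and on the absence of a further schedule in the guidance document not seen here. The effect is confined to the overall toxicity summaries. Sample size, the response test and the run-in rule do not change. The correction should be made because safety is the primary endpoint and most of the contacts needed are already planned.

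**What to change.** 1. In flow charts 6.0 and 6.1 and in Sections 7.1.5.4 and 7.1.5.4.1, add an SAE/ECI review to the 8-weekly follow-up visits and to the first survival call.
2. State that the first survival call is counted from the last dose, and time it at or just after day 90 for patients whose window is still open. For patients who started new therapy earlier, the call asks about events up to that start.
3. For patients who stop without progression, either add a brief call at day 90 or ask at the next imaging visit (about day 112) about events up to day 90.
4. As a clarification only, state in Section 7.2 that the recording period for ECIs is the 90 days of Section 7.2.3.2, and align Section 7.1.2.1 with the revised flow charts.

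The cost is a few extra minutes per contact, one short new call for some patients if the day-90 option is chosen, and possibly slightly higher reported late-event rates. Asking at day 112 avoids the extra call but relies on longer recall. Questions will not find a laboratory abnormality without symptoms, and the safety report should state that limit.

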7.2 Assessing and Recording Adverse Events

An adverse event is defined as any untoward medical occurrence in a patient or clinical investigation subject administered a pharmaceutical product and which does not necessarily have to have a causal relationship with this treatment. An adverse event can therefore be any unfavorable and unintended sign (including an abnormal laboratory finding, for example), symptom, or disease temporally associated with the use of a medicinal product or protocol-specified procedure, whether or not considered related to the medicinal product or protocol-specified procedure. Any worsening (i.e., any clinically significant adverse change in frequency and/or intensity) of a preexisting condition that is temporally associated with the use of the Merck's product, is also an adverse event.

Changes resulting from normal growth and development that do not vary significantly in frequency or severity from expected levels are not to be considered adverse events. Examples of this may include, but are not limited to, teething, typical crying in infants and children and onset of menses or menopause occurring at a physiologically appropriate time.

Merck product includes any pharmaceutical product, biological product, device, diagnostic agent or protocol-specified procedure, whether investigational (including placebo or active comparator medication) or marketed, manufactured by, licensed by, provided by or distributed by Merck for human use.

Adverse events may occur during the course of the use of Merck product in clinical trials or within the follow-up period specified by the protocol, or prescribed in clinical practice, from overdose (whether accidental or intentional), from abuse and from withdrawal.

Adverse events will be recorded from the time the first dose of either vorinostat or MK-3475 is administered through 30 days following cessation of treatment and at each examination on the Adverse Event case report forms/worksheets. After 30 days, adverse events related to either MP-3475 or vorinostat will be followed until resolution or stabilization of the AE or until the beginning of a new anti-neoplastic therapy, whichever occurs first. The reporting timeframe for adverse events meeting any serious criteria is described in section 7.2.3.1.

Only adverse events that meet the following definition will be recorded.

- All grade 3 and higher adverse events
- Any adverse event the requires a dose reduction or dose delay of either MK-3475 or vorinostat
- All adverse events that meet Merck's definition of Event of Clinical Interest (refer to the separate Pembrolizumab ECI guidance document)

7.2.1 Definition of an Overdose for This Protocol and Reporting of Overdose to the Sponsor and to Merck

For purposes of this trial, an overdose will be defined as any dose exceeding the prescribed dose for MK-3475 by 20% over the prescribed dose. No specific information is available on

the treatment of overdose of MK-3475. In the event of overdose, MK-3475 should be discontinued and the subject should be observed closely for signs of toxicity. Appropriate supportive treatment should be provided if clinically indicated.

If an adverse event(s) is associated with ("results from") the overdose of a Merck product, the adverse event(s) is reported as a serious adverse event, even if no other seriousness criteria are met.

If a dose of Merck's product meeting the protocol definition of overdose is taken without any associated clinical symptoms or abnormal laboratory results, the overdose is reported as a non-serious Event of Clinical Interest (ECI), using the terminology "accidental or intentional overdose without adverse effect."

An overdose for vorinostat will be defined as any dose of study drug(s) that is 10% or more over the prescribed dose per cycle as described in the study protocol. No specific information is available on the treatment of overdose of vorinostat. There is no specific antidote for vorinostat overdose. In clinical studies, the highest total daily doses tested were 600 mg (once daily), 800 mg (400 mg twice daily) and 900 mg (300 mg three times daily). In four patients who took more than the recommended study dose (without exceeding the highest doses tested), no adverse experiences were reported. The pharmacological effects may be prolonged after serum levels of active vorinostat are no longer present. It is not known if vorinostat is dialyzable. In the event of overdose, vorinostat should be held and the patient should be observed closely for signs of toxicity. As clinically indicated, appropriate supportive treatment should be provided, if applicable.

All reports of overdose with and without an adverse event must be reported within 24 hours to the Sponsor and within 2 working days hours to Merck Global Safety. (Attn: Worldwide Product Safety; [contact])

